1. DESCRIPTION OF THE STUDY

1.1. Introduction

Hemophilia A is an X-linked recessive disease in which clotting factor VIII (FVIII) is deficient or inactive. Patients with a low level of FVIII have an increased tendency to bleed. When the levels of FVIII are very low (≤2% of normal), spontaneous bleeding episodes may occur. Infusing patients with a concentrated formulation of the missing FVIII protein can control the bleeding. ReFacto (moroctocog alfa) is a commercially available B-Domain Deleted Recombinant FVIII. A modified manufacturing process has been developed to produce ReFacto with an albumin free cell culture (AF-CC) that eliminates the use of all human or animal-derived proteins and therefore enhances the overall viral safety for patients. This product is referred to as moroctocog alfa (AF-CC) and this nomenclature will be used through this statistical analysis plan.

While prophylaxis therapy with FVIII products has increasingly been prescribed worldwide, direct clinical information on optimal prophylaxis dosing strategies is limited. Therefore, this study will directly evaluate the efficacy of moroctocog alfa (AF-CC) prophylaxis to reduce bleed rates relative to moroctocog alfa (AF-CC) on-demand therapy, and will compare the clinical outcomes of a high- versus a low-frequency dosing regimen in a randomized crossover design. In addition, younger hemophilia A patients may respond differently to FVIII therapy compared with older children and adults. Therefore, this study will also characterize the pharmacokinetics (PK) of moroctocog alfa (AF-CC) in children younger than 16 years of age.

1.2. Objectives of the Study

Primary Objective: To demonstrate that moroctocog alfa (AF-CC) prophylaxis reduces annualized bleeding rates (ABRs) relative to on-demand therapy.

Secondary Objectives:

- To assess the effect of a high (25 IU/kg every other day)- versus low (45 IU/kg twice per week)- frequency dosing schedule on the efficacy of moroctocog alfa (AF-CC) prophylaxis.
- To characterize the PK of moroctocog alfa (AF-CC) in children younger than 16 years of age.
- To describe moroctocog alfa (AF-CC) efficacy and safety in children, including characterization of the incidence of "less-than-expected therapeutic effect".

1.3. Design

This 2-segment study will be conducted as a multicenter, open-label, stratified, randomized evaluation of moroctocog alfa (AF-CC) in approximately 72 pediatric subjects (<16 years of age) with moderately severe to severe hemophilia A.

For segment 1, all subjects will use moroctocog alfa (AF-CC) in 1 of 2 treatment settings: on-demand (OD) therapy for 6 months (OD cohort) or prophylaxis for a 12-month period (RP cohort). Subjects who practice prophylaxis will be randomized to one of two regimens. The two prophylaxis treatment regimens, each delivering approximately 90 IU/kg/week, but differing in dosing schedule, will be:

A: 45 ± 5 IU/kg, administered twice a week

B: 25 ± 5 IU/kg, administered every other day

For segment 2, all subjects will use moroctocog alfa (AF-CC) for a 12-month period of prophylaxis treatment. Subjects who practiced on-demand therapy during segment 1 will practice prophylactic regimen B, defined above. Subjects who practiced prophylaxis during segment 1 will crossover to the other prophylactic treatment. A subset of subjects will participate in assessments for moroctocog alfa (AF-CC) PK characterization. This subset of subjects will undergo a baseline PK assessment, receiving a single open-label dose of moroctocog alfa (AF-CC) (50 \pm 5 IU/kg) with blood sampled for FVIII activity measurements before and at 0.5, 8, 24, 28 (optional), and 32 hours after the infusion.

Subjects on on-demand therapy for segment 1: Subjects who practice on-demand therapy at the time of the screening visit may continue to practice on-demand therapy with moroctocog alfa (AF-CC) in segment 1 (6-month period). These subjects will then practice prophylaxis regimen B for their 12-month period (segment 2) of treatment.

Subjects on prophylaxis treatment for segment 1: Subjects who are not assigned to the ondemand cohort in segment 1 will practice prophylaxis with moroctocog alfa (AF-CC) for both segments of the study and will be randomized in a 1:1 ratio to 1 of 2 treatment sequences (AB or BA) for a crossover evaluation of moroctocog alfa (AF-CC). Thus, subjects who practiced prophylaxis regimen A during segment 1 will crossover to prophylactic regimen B in segment 2 and vice versa. Randomization of these subjects will also be stratified by hemophilia A severity: FVIII activity <1% or 1-2% (central laboratory screening result).

During prophylaxis (segment 1 and/or segment 2), a subject's treatment will be escalated to a higher intensity comprised of the most intensive components of both regimens A and B (45 ± 5 IU/kg, administered every other day) if criteria justifying regimen escalation are met. During prophylaxis, subjects will also use moroctocog alfa (AF-CC), as needed, for the treatment of bleeds (ie, on-demand), should they occur.

Clinical and laboratory examinations, including assessments for FVIII inhibitor development, will be conducted during the course of the study.

1.3.1. Description of Subject Population

Subjects will be selected from approximately 40 sites. A legal acceptable representative of the subject must participate in the informed consent/assent process and sign and date the informed consent/assent form before any study procedures or screening activities are performed. The following key conditions are required for enrollment in this study. (See protocol for a complete listing of inclusion and exclusion criteria).

Main Inclusion Criteria:

- Male patients with moderately severe to severe hemophilia A (FVIII: $C \le 2\%$) by **both** the local laboratory and the central laboratory at screening.
- A negative FVIII inhibitor by **both** the local laboratory and the central laboratory at screening.
- Age <16 years at time of screening visit (study visit 1).
- Previous experience of FVIII therapy (≥20 exposure days to any FVIII replacement product). [Protocol Amendment 4 changed this requirement from ≥50 exposure days to ≥20 exposure days].

Additional Inclusion Criteria for subjects participating in the PK assessments:

- *Male patients with FVIII:* $C \le 1\%$ *confirmed by the central laboratory at screening.*
- Age < 16 years at time of PK assessment (study visit 2).
- *The subject's size is sufficient to permit PK-related phlebotomy.*
- The subject is able to comply with the PK-related procedures and required washouts.

Main Exclusion Criterion:

• A history of FVIII inhibitor (clinical or laboratory-based assessment).

1.3.2. Method of Treatment Assignment

Allocation of subjects to treatment assignments will be performed using an interactive voice or web-based response system. Assignment to treatment groups is a function of the following variables: eligibility to undergo the PK assessments and investigator-assignment based on previous FVIII treatment. Based on the study design, two subject groups (ie, cohorts), labeled for their segment 1 treatment, are included in this study: 1) OD subjects and 2) RP subjects. Subjects undergoing PK assessments could be from either cohort. See SAP Section 1.3.3.

At the beginning of segment 1, a subset of eligible subjects will participate in the PK assessment. Also at the beginning of segment 1, the investigator can choose to assign subjects to the OD subject group if the subject was previously practicing on-demand therapy, otherwise subjects will enter the RP subject group. Thus, the OD and RP subject groups are mutually exclusive, however, all of the PK subjects will also belong to either the OD or the RP subject group.

1.3.3. Description of Subject Groups

PK Subjects: Eligible subjects from either subject group will participate in assessments to characterize the pharmacokinetics (PK) of moroctocog alfa (AF-CC).

OD Subjects: Subjects who practice on-demand therapy at the time of the screening visit may continue to practice on-demand therapy with moroctocog alfa (AF-CC) in segment 1. These subjects will then practice prophylaxis regimen B using moroctocog alfa (AF-CC) for their second segment (a 12-month period) of treatment. Dropouts after randomization will not be replaced.

RP Subjects: Subjects who are not assigned to the on-demand cohort in segment 1 will practice prophylaxis with moroctocog alfa (AF-CC) for both segments of the study and will be randomized in a 1:1 ratio to 1 of 2 treatment sequences (AB or BA). Subjects who practiced prophylaxis regimen A during segment 1 will crossover to prophylactic regimen B in segment 2 and vice versa. Dropouts after randomization will not be replaced.

1.3.4. Interim Analysis

An independent data-monitoring committee (DMC) will periodically review data from the study to ensure subject safety, with review intervals of approximately every 6 months.

Prior to study completion, selected (safety, efficacy and/or PK) data from this study may be summarized and reported to regulatory authorities to support regulatory submissions or requests. The analyses for these summaries would be based on descriptive statistics. Per discussions with the FDA, a final report for the OD cohort will be submitted comparing prophylaxis efficacy and safety versus on-demand therapy according to SAP Section 3.3. Additionally, after approximately 38 evaluable RP subjects, who practiced prophylaxis for both segment 1 and segment 2, complete the study, a final report for the RP cohort will be submitted. See SAP Section 3.2 for more detail on analysis populations.

1.4. Sample Size Determination

Approximately 72 subjects will be enrolled in this study at approximately 40 sites. Subjects withdrawn from the study will not be replaced, regardless of the reason for withdrawal.

The study was designed to meet three objectives: the primary objective of comparing ABRs while on on-demand therapy versus prophylaxis, and the secondary objectives of comparing ABRs while on high- versus low-frequency prophylaxis and PK characterization. Twenty-four (24) subjects (the OD subject group) will contribute to the comparison of ABR in the on-demand versus prophylaxis treatment settings; 48 subjects (the RP subject group) will contribute to the comparison of ABR in the 2 prophylaxis regimens (A and B). From the total of 72 subjects, a subset of approximately 23 PK subjects (meeting specific criteria) is needed for PK assessments for the objective of PK characterization. Additional information regarding the calculation of each of these sample size estimates is provided below.

1.4.1. Sample Size Estimation Comparing the Annualized Bleed Rates of Prophylaxis to On-Demand Therapy

The primary objective of this study will be to demonstrate a decrease in ABR while on prophylaxis treatment compared to while on on-demand therapy. In a previous Wyeth moroctocog alfa pediatric study, protocol 3082A1-301-WW (study 301), a reduction in the ABR was observed for subjects during their periods of prophylaxis (≥ 2 infusions per week) compared to their periods of on-demand treatment (reduction of 5.7 ± 6.9 bleeds per year, [11.85 to 6.15 bleeds per year], ABR decrease of 48%, N=39). Based upon this experience, a more conservative decrease in ABR of 40% (corresponding to a mean change of 4.75 bleeds per year) and a standard deviation of 7 were selected for use in power calculations for the comparison of ABRs in the on-demand versus prophylaxis setting for this study. A 40% treatment effect difference is considered to constitute a clinically significant reduction in ABR for sample size estimation. Using a paired t-test and the above assumptions, it was determined that a sample size of 18 OD subjects will provide 80% power to detect such a difference using a 2-sided alpha level of 0.05. Based upon prior recombinant FVIII clinical studies, an attrition rate of up to approximately 25% may be expected. Therefore, approximately 24 OD subjects are required to ensure that 18 are evaluable for the comparison of ABRs in the on-demand versus prophylaxis setting.

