1. The first interim CSR presented safety, efficacy and baseline data for subjects at Site PP separately from data for subjects at other sites, due to serious breaches of GCP compliance by the investigator and study staff at Site PP pertaining to data integrity. As implemented in the second Interim CSR, in the Final CSR, safety, efficacy and baseline summary data will be presented excluding Site PP with the exception of protocol deviations, recovery/pharmacokinetic data, and inhibitor incidence, which include all sites.

- 2. As determined for the second Interim CSR for the study's primary endpoint analysis in the OD cohort only, a linear mixed-effects model with unstructured variance-covariance matrix provides a more robust model for the comparison of annualized bleeding rate (ABR) given the nature of the study data, while still controlling for the same factors as specified in the SAP ANOVA model. This model allows for the inclusion of all intent-to-treat (ITT) subjects with ABR data and also takes into account the correlation between the 2 within-subject measurements of ABR at each segment. Because all enrolled subjects had severe (<1%) hemophilia at baseline (ie, just one level of the factor was present and therefore not informative), hemophilia severity is not included as a factor in the model as planned. In the Final CSR, the estimates of the ABR for each regimen (segment) and for the difference as well as the corresponding two-sided 95% confidence intervals (CIs) will be reported using the linear mixed-effects model described above rather than as described in SAP Section 3.3.1.2.

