- 3. As implemented in the second Interim CSR as per FDA Written Response dated 28 January 2016 (CRMTS #10042, BL 125264/1540), supportive analyses will also be performed for the ITT population for the Final CSR. A paired t-test will be used to test the within-subject change in ABR for the subjects who will be evaluated with both OD and routine prophylaxis (RP) dosing during the study. In addition, a one-sided 95% CI for the ratio of the arithmetic means for ABR during RP over the ABR during OD treatment will be calculated. Ogawa's parametric confidence interval for the ratio of two paired means¹ assumes the ABR is bivariate normally distributed for RP and OD treatments and will be calculated using R statistical software (version 3.2.3). If the one-sided 95% upper confidence bound is ≤0.5, then this will confirm that the ABR during RP treatment was at least 50% lower than that observed during OD treatment.
- 4. In accordance with FDA correspondence dated 27 January 2017 (IND 10040/246) stating that a non-inferiority clinical margin M2 of 3 bleeds or fewer per year may be adequate, equivalence between the 2 RP regimens will be declared if the limits of the 90% two-sided confidence interval fall wholly within the interval of (-3, 3) bleeds per year, rather than protocol/SAP specified (-4, 4) (SAP Sections 1.4.2 and 3.3.2.2).
- 5. Per FDA correspondence dated 27 January 2017 (IND 10040/246), incidence rate of inhibitor development will be additionally described by number of prior exposure days at study entry. For this assessment, based on the risk of the inhibitor development according to the number of exposure days, minimally treated patients (MTPs) will include those who had accrued 20 to <50 exposure days to any FVIII replacement product prior to enrollment into Protocol B1831001. Note: Previously treated patients (PTPs) are patients who have received FVIII replacement therapy. Prior to Protocol Amendment 4, PTPs were defined for the purposes of the study as those who had accrued at least 50 exposure days (EDs) to any FVIII replacement product prior to study enrollment. To improve enrollment, in Protocol Amendment 4 (dated 15 September 2009) this number was decreased to at least 20 prior EDs for inclusion in the study. SAP Section 3.4.2.1 refers to Inhibitor Development.

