1.4.2. Sample Size Estimation Comparing High versus Low Prophylactic Dosing

A secondary objective is to evaluate the effect of a high versus low dosing frequency schedule on prophylactic efficacy. Data from the previously mentioned moroctocog alfa study 301 revealed an ABR of 5.7 ± 5.2 (N=26) in subjects receiving a high-frequency prophylaxis regimen (3 infusions per week) compared to an ABR of 7.1 ± 4.1 (N=13) in patients receiving a lower-frequency prophylaxis regimen (2 infusions per week). Assuming an intraclass correlation of 30% and a standard deviation of 6 bleeds per year based on the above study results, a within-subject standard deviation of 5 bleeds per year was used for sample size calculations for the comparison between the high- and low-frequency prophylaxis regimens. Given this, 36 RP subjects are needed to provide 80% power to demonstrate equivalence of the two regimens. The two regimens will be considered equivalent if the limits of the 90% two-sided confidence interval for the difference in observed mean ABRs falls wholly within the interval of -4 to 4 bleeds per year. Allowing for an attrition rate of 25%, approximately 48 RP subjects should be enrolled to support this objective.

Based on a sample size re-estimation using data from this ongoing study, a difference of means of 1.3 bleeds per year between the two protocol-defined prophylaxis regimens (A and B) with a corresponding standard deviation of the difference of 6.5 was obtained requiring 38 subjects to provide 80% power to demonstrate equivalence of the two regimens. Allowing for an attrition rate of 30%, approximately 56 RP subjects need to be enrolled. The two prophylaxis regimens will be considered equivalent if the limits of the 2-sided 90% confidence interval for the difference in observed mean ABRs fall wholly within the interval defined by fewer than 4 bleeds per year. See the Summary of Changes to Planned Analyses for the Final CSR (Item 4) for further discussion.

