APPENDIX C: CHANGES IN THE PLANNED ANALYSES FROM INTERIM CSRS

Changes in the Planned Analyses were described in Section 9.8.2 within each of the 2 interim CSRs for this study.

Interim CSR 1 (dated 07 November 2013), in support of the Pediatric 2013 sBLA

9.8.2 Changes in the Planned Analyses: The analyses reported in here are limited and restricted to descriptive statistics. Safety, efficacy and baseline data for subjects at Site are presented separately from data for subjects at other sites, due to serious breaches of Good Clinical Practice (GCP) compliance by the investigator and study staff at Site pertaining to data integrity. Pharmacokinetic (PK) data are objective and it is believed that interpretation of these data is not compromised by the deficiencies noted at Site PPD The PK data which were collected from subjects from this site are, therefore, presented and included in the summary for the study.

Interim CSR 2 (dated 11 April 2016), in support of the Prophylaxis 2016 sBLA

9.8.2 Changes in the Planned Analyses: The previous interim CSR presented safety, efficacy and baseline data for subjects at Site PP separately from data for subjects at other sites, due to serious breaches of GCP compliance by the investigator and study staff at Site PP pertaining to data integrity. In this second interim CSR, safety, efficacy and baseline summary data are presented excluding Site PP with the exception of protocol deviations, and inhibitor incidence, which include all sites.

As per the SAP Section 3.3, efficacy data on and subsequent to the date of inhibitor development was not to be included in the efficacy analyses. However, with the exception of the following summary tables: CSR Section 14.2, Table 14.2.4.3, Table 14.2.4.4, Table 14.2.5.1, and Table 14.2.5.2, the efficacy summary tables did not exclude bleeds occurring after inhibitor development. (This has been corrected for the Final CSR).

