During the programming for the primary endpoint, prior to the data snapshot and prior to analysis, it was determined that a linear mixed-effects model with unstructured variance-covariance matrix would provide a more robust model for the comparison of annualized bleeding rate (ABR) given the nature of the study data, while still controlling for the same factors as specified in the SAP ANOVA model. This model allows for the inclusion of all intent-to-treat (ITT) subjects with ABR data including the 1 subject with Segment 1 (on-demand [OD] regimen) only at the time of the data cut-off for this second interim analysis and also takes into account the correlation between the 2 within subject measurements of ABR at each segment. Because all enrolled subjects had severe (<1%) hemophilia at baseline (ie, just one level of the factor was present and therefore not informative), hemophilia severity was not included as a factor as planned. The estimates of the ABR for each regimen (segment) and for the difference as well as the corresponding two-sided 95% confidence intervals (CIs) are reported using the linear mixed-effects model.

Supportive analyses were also performed for the ITT population. A paired t-test was used to test the within-subject change in ABR for the 8 subjects who were evaluated with both OD and routine prophylaxis (RP) dosing during the study. In addition, a one-sided 95% CI for

the ratio of the arithmetic means for ABR during RP over the ABR during OD treatment was calculated using R statistical software (version 3.2.3). If the one-sided 95% upper confidence bound was \leq 0.5, then this confirmed that the ABR during RP treatment was at least 50% lower than that observed during OD treatment.

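### SAP 1.4 and 1.4.1 give 24 OD subjects, 18 evaluable and 80% power for the primary objective without saying that the OD cohort is closed or how many pairs remain

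*SAP*

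**What the plan says.** SAP 1.4 describes the OD contribution in the future tense: "Twenty-four (24) subjects (the OD subject group) will contribute to the comparison of ABR in the on-demand versus prophylaxis treatment settings". SAP 1.4.1 then gives the power: "Using a paired t-test and the above assumptions, it was determined that a sample size of 18 OD subjects will provide 80% power", for a mean change of 4.75 bleeds per year with SD 7 at a two-sided 5% level. It enrols 24 to allow for 25% attrition.

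The protocol synopsis and protocol 22.7 carry the same calculation. They put the 24 in the past tense as a plan and add that, with OD enrolment closed, all available data will be analysed. SAP Appendix B lists the closure among the main changes of Amendment 10.

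SAP Appendix C, on the second interim CSR, says that a paired t-test was run "for the 8 subjects who were evaluated with both OD and routine prophylaxis (RP) dosing during the study". It says that the mixed model used all ITT subjects with ABR data, "including the 1 subject with Segment 1 (on-demand [OD] regimen) only at the time of the data cut-off". One site was left out for GCP breaches: "In this second interim CSR, safety, efficacy and baseline summary data are presented excluding Site PP". Item 1 of the SAP's Summary of Changes applies the same rule to the Final CSR: "efficacy and baseline summary data will be presented excluding Site PP". Item 2 makes a linear mixed-effects model the method for the primary comparison. Item 3 adds a supportive analysis: "A paired t-test will be used to test the within-subject change in ABR".

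**The concern.** A reader who takes SAP 1.4 and 1.4.1 on their own will believe that the primary objective rests on 24 contributors, 18 of them evaluable, with 80% power. The SAP's own appendix points to about half that number of pairs or fewer. None of the eight items in the Summary of Changes revises the OD size or power.

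The neighbouring section was treated differently. SAP 1.4.2, for the RP cohort, keeps its first calculation but adds an update, "Based on a sample size re-estimation using data from this ongoing study", and a pointer to Item 4. The OD section has neither. The Overview keeps out of the SAP body only changes determined after Amendment 10 was implemented. The closure is part of Amendment 10, so that rule does not explain its absence.

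At stake is what is claimed about the size and precision of the comparison behind the primary objective, for which a separate OD report to the FDA is planned.

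**Working it through.** **Inputs.** Change 4.75, SD of the change 7, two-sided 5%, 80% power, 25% attrition, paired t-test (all SAP 1.4.1). Pairs at the second interim CSR: 8, plus 1 subject with Segment 1 only (SAP Appendix C). The final number of pairs is in neither document, so a range is shown.

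**Step 1: reproduce the plan's figure.** Normal approximation: n = [(1.960 + 0.842) × 7 / 4.75]² = 17.05, rounded up to 18. Power at 18 by the same approximation is Φ(4.75√18/7 − 1.960) = Φ(0.919) = 82%. Enrolment: 18/0.75 = 24. Both planned numbers reproduce.

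**Step 2: the test that the SAP names.** For a paired t-test, power is the probability that a noncentral t variable with n − 1 degrees of freedom and noncentrality λ = 4.75√n/7 falls beyond ±t(0.975, n − 1). The half-width of the 95% CI is t(0.975, n − 1) × 7/√n.

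| Pairs | λ | t | Power | 95% half-width (bleeds/year) |
|---|---|---|---|---|
| 8 | 1.92 | 2.365 | 38% | 5.9 |
| 9 | 2.04 | 2.306 | 43% | 5.4 |
| 12 | 2.35 | 2.201 | 57% | 4.4 |
| 16 | 2.71 | 2.131 | 72% | 3.7 |
| 18 | 2.88 | 2.110 | 77% | 3.5 |
| 20 | 3.03 | 2.093 | 82% | 3.3 |

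At 19 pairs power is 79.9%, so 20 is the first number to reach 80%. The half-widths take the sample SD to be exactly 7. Averaged over sampling variation in the SD, the value at 8 pairs is nearer 5.6.

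**Step 3: what 8 or 9 pairs could detect.** With SD 7, the change detectable with 80% power is 8.1 bleeds per year at 8 pairs and 7.5 at 9, against the planned 4.75.

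**Step 4: a more favourable assumption.** With the earlier study's observed reduction of 5.7 and SD 6.9, power is 52% at 8 pairs and 59% at 9.

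**Step 5: other numbers in the same paragraph.** SAP 1.4 totals 24 + 48 = 72 subjects; the protocol has 24 + 56 = 80. SAP 1.4.2 gives 56 for the RP cohort. SAP 1.4 also needs about 23 PK subjects, while SAP 1.4.3 declares a PK sample size not applicable.

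**The case against.** The strongest reply is that nobody is misled. The SAP Overview describes the sizes as originally planned ones, the protocol carries the closure sentence twice, and Appendix B records the closure. A closed cohort has nothing to re-estimate. The achieved precision will be visible from the confidence intervals in Items 2 and 3. The comparison has already been run once for the second interim CSR, so a planning-stage power adds little. The power figures here also describe the supportive paired t-test, not the mixed model of Item 2.

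Much of this stands. It makes the point one of outdated text and disclosure, and any restated power must be labelled as that of the paired t-test. It does not remove the point: SAP 1.4 and 1.4.1 carry no label, no closure sentence and no pointer, and neither document corrects the stated size or power.

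Three stronger readings go beyond the documents:

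- A reader might infer that the final comparison will have only 8 or 9 pairs. The data cut-off, the OD count at the excluded site and OD dropouts are not given, so this is not established.
- A reader might infer that the sample size was miscalculated. It was not: 18 is the normal-approximation answer, and 77% against 80% is a secondary remark.
- A reader might infer that protocol 11.4, which says approximately 24 OD subjects were enrolled, is false. It is not reconciled with 8 plus 1, but an interim count with a site removed cannot refute it.

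**Conclusion.** The point holds as a defect of outdated text on the primary objective. SAP 1.4 and 1.4.1 state a size and power that the SAP's own appendix does not bear out, and they omit the caveat that the protocol attaches to the same calculation.

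If the final analysis has the 8 or 9 pairs that Appendix C suggests, planned power falls from the stated 80% to about 38% or 43%, and the expected half-width exceeds the 4.75 effect itself. These figures rest on the SAP's assumed change and SD and on an inferred count. The shortfall does not hinge on exactly 8: even 16 pairs would give 72%. Low planned power does not invalidate an observed result, and the hypothesis, model and population are unaffected.

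**What to change.** In SAP 1.4 and 1.4.1:

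- Label 24, 18 and 80% as the original plan. Do the same for 72, 48 and 23 in that paragraph.
- Add the protocol's statement that OD enrolment is closed and all available data will be analysed.
- State the actual number of OD pairs available after the site exclusion, with a cross-reference to Appendices B and C.
- Restate power or expected CI half-width at that number (38% and 5.9 if 8 pairs; 43% and 5.4 if 9). Say that it describes the supportive paired t-test of Item 3 and that the primary model is the mixed model of Item 2.
- Secondary: note that 18 is the normal-approximation size, and that the exact paired t-test gives 77% at 18 and needs 20 for 80%.

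Protocol 11.4 needs only to have its count reconciled with the SAP's actual OD number. The cost is wording plus one verified count, and the stated power becomes less favourable. No further enrolment and no change to the analysis is called for.

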# 11.4. Approximate Number of Subjects

Approximately 56 subjects will be enrolled in the RP cohort of this study at approximately 40 sites globally. Approximately 24 subjects were enrolled in the OD cohort. Enrollment in the OD cohort has been closed. Subjects withdrawn from the study will not be replaced, regardless of the reason for withdrawal.

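### SAP 1.3 and 1.4 still state the superseded sizes (72 in total, 48 RP) as the current plan, against 80 and 56 elsewhere; separately, the original 36 does not reproduce under the 90% CI printed beside it

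*SAP*

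**What the plan says.** The SAP overview states that version 5.0 takes in the protocol changes through Amendment 10, and that both the original sizes and the re-estimation are shown.

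- SAP 1.3 (Design) describes the study as a "randomized evaluation of moroctocog alfa (AF-CC) in approximately 72 pediatric subjects". The same sentence already carries the Amendment 10 age limit of under 16 years.
- SAP 1.4 opens with "Approximately 72 subjects will be enrolled in this study at approximately 40 sites". It divides them into 24 OD and 48 RP subjects and says that "48 subjects (the RP subject group) will contribute to the comparison of ABR in the 2 prophylaxis regimens (A and B").
- SAP 1.4.2 gives the first calculation: "Given this, 36 RP subjects are needed to provide 80% power to demonstrate equivalence of the two regimens". It uses a within-subject SD of 5, a 90% CI and limits of -4 to 4, and inflates to 48 for 25% attrition. The next paragraph gives the re-estimation: difference 1.3, SD of the difference 6.5, 38 evaluable. It concludes: "Allowing for an attrition rate of 30%, approximately 56 RP subjects need to be enrolled".
- Protocol 11.4: "Approximately 56 subjects will be enrolled in the RP cohort of this study at approximately 40 sites globally". The protocol synopsis and study overview give 80 in total (56 RP plus 24 OD). Protocol 22.7 repeats both calculations.
- SAP 1.3.4 ties the RP report to about 38 evaluable RP subjects.
- Item 4 of the SAP's Summary of Changes replaces the ±4 limits by ±3 for the final report.

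**The concern.** The SAP gives two enrolment targets for one comparison. Sections 1.3 and 1.4 state only the old one, in the future tense, without calling it original and without their own cross-reference to the re-estimation. A reader who stops at 1.4 takes away 48 enrolled and 72 in total, and also that all 48 enter the regimen comparison. The 48 already included a 25% allowance for attrition over 36 evaluable, and withdrawn subjects are not replaced, so the last statement is wrong even for the old plan.

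The original 36 has a different problem. Its stated power cannot be checked, because no true difference is given, and the natural choice of zero does not lead to 80% under the printed CI level. At stake is whether the SAP's account of its own sample size can be relied on when the equivalence result is reported.

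**Working it through.** **Method.** Equivalence is declared if the 90% CI for the mean paired difference, based on t with n-1 degrees of freedom (SAP 3.3.2.2), lies within ±M. Power is the probability that |D̄| + t(0.95, n-1)·S/√n < M, computed exactly with D̄ normal and integration over the sampling distribution of S.

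**Step 1: reproduce the re-estimation.** Inputs from SAP 1.4.2: difference 1.3, SD of difference 6.5, M = 4, 90% CI.

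- Normal approximation: n ≈ [6.5 × (1.645 + 0.842) / (4 - 1.3)]² ≈ 35.8.
- Exact: n = 38, power 80.7%. The stated 38 reproduces.
- Enrolment: 38 / 0.70 = 54.3, so 55, which the plan gives as about 56. Conversely, 56 × 0.70 = 39.2 evaluable.
- Totals: 24 + 56 = 80 (protocol); 24 + 48 = 72 (SAP 1.3 and 1.4).

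**Step 2: what 48 enrolled would deliver with the same inputs.**

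| Attrition | Evaluable | Power |
|---|---|---|
| 30% (re-estimation) | 48 × 0.70 = 33.6, so 33 or 34 | 75.3% or 76.5% |
| 25% (original plan) | 48 × 0.75 = 36 | 78.7% |
| Re-estimated target | 38 | 80.7% |

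**Step 3: the original 36.** Inputs from SAP 1.4.2 and Protocol 22.7: SD 6 and intraclass correlation 0.30, so the within-subject SD is 6 × √0.70 = 5.02, used as 5. The SD of the paired difference is 5 × √2 = 7.07, and M = 4. The true difference is not stated, so it is varied here.

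| CI level | True difference (assumed) | Power at n = 36 | n for 80% |
|---|---|---|---|
| 90% | 0 | 90.8% | 29 |
| 90% | 0.5 | 87.9% | 30 |
| 90% | 1.0 | 79.7% | 37 |
| 90% | 1.4 (7.1 - 5.7, study 301) | 69.6% | 48 |
| 95% | 0 | 82.0% | 35 |

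Under the 90% CI, 36 gives exactly 80% only at a true difference of about 0.98, a value found nowhere in the documents. Under a 95% CI and zero difference, the required n is 35, or 36 if the within-subject SD is left at 5.02. SAP Appendix B records that Amendment 10 corrected the CI for this comparison from 95% to 90%. The enrolment step does reproduce: 36 / 0.75 = 48.

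**Step 4: the ±3 margin of Item 4.** With difference 1.3 and SD 6.5, 38 evaluable give 46.6% power, and 92 would be needed for 80%. With zero difference, 38 give 74.9%.

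**The case against.** The strongest reply is that the overview says original and re-estimated sizes both appear, that SAP 1.4 sends the reader to the detail below it, where 56 stands, and that Appendix B records the revision. The protocol governs enrolment at 56, and the RP report waits for about 38 evaluable subjects. Nothing suggests that anyone would enrol to 48. On this view the old numbers are harmless leftovers.

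Much of this stands. It fully covers SAP 1.4.2, where 36/48 is plainly a first calculation followed by its replacement. It also limits the consequence: a reader might infer that the trial is being run at 48, and the documents do not support that. It does not cover SAP 1.3 and 1.4, which state 72 and 48 as the plan, and the under-16 age limit beside the 72 shows that the passage was only partly updated.

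A second tempting inference is that 36 was underpowered. That is not shown. With zero difference it exceeds 80%; it falls below only above a difference of about 1.0. The 1.4 seen in study 301 was not adopted as a design assumption, and Protocol 22.7 itself notes that treatment there was neither randomized nor controlled. What holds is that the figure does not reproduce as printed.

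Third, the 75–77% in Step 2 pairs the old enrolment with the new attrition rate. At the 25% that belonged to the 48, the loss is about 2 points against 38 (78.7% versus 80.7%).

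**Conclusion.** The inconsistency is real and modest. SAP 1.3 and 1.4 are wrong as written: the RP enrolment figure is 8 too low (48 against 56), the total is 8 too low (72 against 80), and enrolled subjects are described as contributing subjects. Taken literally, 48 enrolled would give about 75–79% power instead of 81%, given the re-estimated difference of 1.3, SD of 6.5, margin of 4 and attrition of 30% or 25%.

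The original 36 does not reproduce 80% under its printed 90% CI, on the assumption of zero difference. It is consistent with the 95% level in force before Amendment 10. That this is where it came from is an inference; no document says so.

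One limit applies to the correction itself. A reader might infer that restoring 56/38 restores 80% power for the final analysis. It does so only at ±4. Under the ±3 limits of Item 4, 38 evaluable give about 47% at the re-estimated inputs.

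**What to change.** - In SAP 1.3 and 1.4, change the total from 72 to 80 and the RP enrolment from 48 to 56, and say that about 38 evaluable RP subjects are expected to contribute to the paired comparison.
- In SAP 1.4.2, label 36/48 as the original, superseded calculation, and state the CI level and true difference it used. If these cannot be recovered from the sponsor's records, say so.
- In SAP 1.4.2, add that 38/56 was sized for the ±4 margin and does not give 80% power under the ±3 margin of Item 4 (about 47% at difference 1.3 and SD 6.5).

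The cost is a few sentences in the SAP and a look-up of the original sizing inputs. No subjects are added, and neither conduct nor the analysis changes. Protocol 22.7 repeats the 36/48 calculation; since the protocol already gives 56 and 80 as its sizes, the same label can wait for the next protocol change made for other reasons.
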